9. STATISTICAL CONSIDERATIONS

9.1 STATISTICAL HYPOTHESES

- Primary Efficacy Endpoint(s):
 - Assessment of infiltration at pre-incision (pre) and infiltration at post-incision (post) associated pain score using a Likert-pain scale. The Likert-like pain scale is a validated, subjective measure for acute and chronic pain. The primary endpoint of pain score measurement will take place on postoperative day 1 (18-24 hr post-surgery, postoperative day 1). Scores are recorded by choosing an integer only number on a 0-10 scale that represents between “no pain” and “worst pain”.
- Secondary Efficacy Endpoint(s):
 - The need for additional narcotic usage over 2 weeks between the 2 arms
 - Compare questionnaires between the initial brief pain inventory questionnaire (pre-surgery) and postoperative brief pain inventory questionnaire

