1 PROTOCOL SUMMARY

1.1 SYNOPSIS

Title:	Clinical effectiveness of pre-incision versus post-incision local anesthetic during laparoscopic/robotic sacrocolpopexy
Study Description:	To compare postoperative narcotic use and pain score with pre-incisional versus post-incisional injection of local anesthetic at trocar sites in robotic/laparoscopic-assisted sacrocolpopexy
Objectives:	
Primary objective: Comparing postoperative Likert pain scale between patients who received pre-incisional versus post-incisional local anesthetic on postoperative day oneSecondary objectives: Total narcotic use over two weeks between patients who received pre-incisional versus post-incisional local anesthetic. To compare the pain levels reported by patients on the brief pain inventory questionnaire at POD14 between the two study groups (pre-incisional vs post-incisional) by two sample t –test or Wilcoxon rank-sum test, where appropriate.

Endpoints:	Primary Endpoint: comparing Likert-pain scale scores between pre-incisional versus post-incisional local anesthetic on postoperative day one Secondary Endpoints: total narcotic use over two weeks between patients who received pre-incisional versus post-incisional local anesthetic and to compare brief pain inventory questionnaires at POD14 between the two study groups.
Study Population:	Sample size – 64 per arm; Female gender, age \geq 18 years old, general health status healthy
Phase:	N/A
Description of Sites/Facilities	Northwell Health sites (Lenox Hill Hospital, Southshore Hospital, Long Island Jewish Hospital, Northshore Hospital, Huntington Hospital, Plainview, Peconic, Mather). No hospital outside of the US.
Enrolling Participants:	Subcutaneous injection of 4-5mL of 0.25% Bupivacaine into skin before or after incision for trocar placement during robotic/laparoscopic- assisted sacrocolpopexy
Description of Study Intervention:	
Study Duration:	18 months
Participant Duration:	2 weeks

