1.2 SCHEMA

Visit 0

- New patient/Surgical discussion Visit
 - Screen potential for inclusion and exclusion criteria
 - If meets criteria
 - Pamphlet provided to patient in regard to study information

Visit 1

- Preoperative visit
 - Discuss study in further detail, answer questions after patient read pamphlet, risks/benefits discussed and offer patient participation
 - If patient consents:
 - First Brief Pain Inventory Questionnaire to fill out prior to surgery. The Narcotic Diary will be given to patient with the instructions to fill out after surgery and to document all narcotic pills used including provided and any additional.
 - If a patient is undecided, then will follow up by phone call prior to surgical day. If she decides after follow up phone call then will have patient sign consent on day of surgery

Visit 2

- Day of surgery

- If patient does not consent at preoperative visit, but decides to participate after follow up phone call:
 - Obtain consent if patient has agreed by phone call (phone call which is after preoperative visit) on the day of surgery
 - Provide narcotic diary and first Brief Pain Inventory Questionnaire to fill out (if patient has not already filled it out previously). Patient only needs to fill out one brief pain inventory questionnaire prior to surgery, the patient should fill this out on the day that they sign the consent for participation (whether it is at the preoperative visit or in the preoperative suite on the day of surgery). The Narcotic Diary will be given to patient with the instructions to fill out after surgery and to document all narcotic pills used including provided and any additional.
- Randomization
 - Arm 1: 64 patients; Arm 2: 64 patients

Visit 3

- Postoperative Day 1
 - Obtain Likert-pain scale score between 18-24 hours post-surgery

Visit 4

- Postoperative Visit (14 days +/- 3 days)
 - Narcotic Diary collected
 - Second Brief Pain Inventory Questionnaire given to patient to complete

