3 OBJECTIVES AND ENDPOINTS

OBJECTIVES	ENDPOINTS	JUSTIFICATION FOR ENDPOINTS
Primary Difference in Likert-pain scale score difference between pre-incision versus post-incision subcutaneous infiltration with 4-5mL 0.25% Bupivacaine at 18-24 hours postoperatively	Likert-pain scale score difference between pre-incision and post-incision subcutaneous infiltration at 18-24 hours postoperatively.	To determine if timing of local anesthetic affects postoperative pain scores.
Secondary To compare total narcotic usage over two weeks	Total number of narcotic tablets used in the first two weeks postoperatively between pre-incision and post-incision subcutaneous infiltration with 4-5mL 0.25% Bupivacaine	To decrease postoperative narcotic usage
Secondary Compare brief pain inventory questionnaire survey score	To compare score levels of the brief pain inventory questionnaire at POD14 between the two study groups	To decrease pain score for patient post surgery

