9.4.3 ANALYSIS OF THE SECONDARY ENDPOINT(S)

Analysis of the secondary outcome:

- The need for additional Narcotic usage over 2 weeks between the 2 arms

All patients will be discharged with 12 standard narcotic pills for managing post-operative pain by needs. However, patients can request additional narcotic pain killers if needed. The needs for extra amount of pain reliever is an indicator of pain level and a secondary aim of the current study.

The need for additional narcotic usage is a binary-coded variable with values of 'yes' or 'no'. The rate/percentage of patients requesting additional narcotic medication will be calculated for each study arm, and compared in a 2 by 2 contingency table format using chi-square test or Fisher's exact test, as appropriate.

- Compare pain scores between each arm at 2 weeks post-operative visit

At the two-week post-operative visit, patients will be asked to fill out the brief pain inventory to indicate their current pain levels, as well as the mildest and worst pain scores within the past 24 hours. The pain scores will also be evaluated by Likert-pain scale (the same pain assessment tool used at POD1. The mean pain scores between the two arms will be compared by a two-sample t-test or a Wilcoxon rank-sum test, where appropriate. Statistical significance between the two arms is considered if the p-value for the tests are <0.05.

9.4.4 9.4.4 SAFETY ANALYSES

Patients will be screening for allergy to or contraindications to study medication. If they meet criteria and consent for the study, then each patient will be monitored for safety in multiple forms. For each patient, vital signs are monitored in the operating room and during recovery until discharge. Electrocardiogram monitoring will also be continuously ongoing in the operating room. Assessment of adverse events throughout hospital stay will be done by review of charts and discussion with other members involved in patient care.

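### The POD14 pain secondary endpoint is defined inconsistently across sections, names no lead BPI score, and includes a two-week Likert score that the two-week collection lists omit

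*Combined protocol and SAP*

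**What the plan says.** All references are to the combined protocol and SAP.

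- **Section 9.1** lists the second secondary endpoint as "Compare questionnaires between the initial brief pain inventory questionnaire (pre-surgery) and postoperative brief pain inventory questionnaire". No arms are named, although the bullet just above it, on narcotic use, does name the two arms.
- **Section 1.1** sets the objective as "To compare the pain levels reported by patients on the brief pain inventory questionnaire at POD14 between the two study groups". **Section 3** has "To compare score levels of the brief pain inventory questionnaire at POD14 between the two study groups". Neither says which BPI score is meant.
- **Section 9.4.3** has patients at the two-week visit "indicate their current pain levels, as well as the mildest and worst pain scores within the past 24 hours", and continues: "The pain scores will also be evaluated by Likert-pain scale (the same pain assessment tool used at POD1". Then "The mean pain scores between the two arms will be compared by a two-sample t-test or a Wilcoxon rank-sum test", and "Statistical significance between the two arms is considered if the p-value for the tests are <0.05".
- **Sections 9.4.2 and 9.4.5** analyse continuous secondary outcomes by a two-sample test. ANCOVA adjusting for baseline is supportive only.
- **Section 1.2** lists two items for Visit 4: collection of the narcotic diary, and "Second Brief Pain Inventory Questionnaire given to patient to complete". The Likert score appears there only at Visit 3, on POD1. The two-week procedures in **section 4.1** and the completion definition in **section 4.4** also name only the diary and the BPI.
- **Section 6.4** mentions a patient log holding a daily pain score, without naming its scale.

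**The concern.** A secondary endpoint should tell the analyst which score is compared, at what time, between whom, and how baseline is used. Here these elements differ between sections or are left open.

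The 9.1 wording, followed literally, contrasts two time points and not two arms. Such a contrast mixes recovery from surgery with everything else that happens in two weeks, and it does not estimate the effect of injection timing. The other sections do compare arms, but none of them picks a score. The BPI yields several, and 9.4.3 names three pain items with no lead item or composite. It then adds a second instrument that staff working from the visit lists would not know to administer.

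At stake is the interpretability of one of the trial's two secondary outcome domains. Several results could each be presented as the POD14 pain result with some support from the text, and the choice could be made after the data are seen.

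**Working it through.** **1. The plan's own figure.** The only sample size stated is for the primary POD1 Likert score (section 9.2: difference 1, SD 2, two-sided alpha 0.05, power 0.80, 1:1 allocation).
- Normal approximation: n per arm = 2 × (1.960 + 0.842)² × 2² / 1² = 62.8, so 63.
- Exact t-test: 63.77, so 64 per arm, with power 0.801.

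The stated 64 per arm reproduces. No figure is given for the POD14 endpoint.

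**2. The definitions side by side.**

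| Section | Contrast | Score | Baseline |
|---|---|---|---|
| 1.1 | arms, POD14 | BPI pain levels, item not named | none stated |
| 3 | arms, POD14 | BPI, item not named | none stated |
| 9.1 | pre-surgery versus postoperative, no arms named | BPI, item not named | one side of the contrast |
| 9.4.3 | arms, two weeks | current, mildest and worst pain, plus Likert | none stated |
| 9.4.2, 9.4.5 | arms | any continuous secondary outcome | supportive ANCOVA only |

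**3. The Likert score at two weeks.** Section 9.4.3 places it at that visit. Sections 1.2 (Visit 4), 4.1 and 4.4 do not list it. The Schedule of Activities in 1.3 has no Likert row at all, even for the POD1 primary endpoint, so its silence carries little weight. The other three places carry the point. The log in 6.4 does not close the gap: its scale is not named, and sections 1.2 and 4.1 describe a diary that records tablets.

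**4. Testing three items at 0.05 each.** Input: per-test level 0.05 from 9.4.3. Assumptions: no true difference, normal test statistics, and a common pairwise correlation r, which the documents do not give.
- Independent: 1 − (1 − 0.05)³ = 1 − 0.857 = 0.143.
- Correlated: 1 − ∫ φ(z) [Φ((c − √r z)/√(1 − r)) − Φ((−c − √r z)/√(1 − r))]³ dz, with c = 1.960. This gives 0.125 at r = 0.5 and 0.109 at r = 0.7.

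**5. Does the role of baseline matter?** As an illustration, borrow the POD1 inputs (difference 1, SD 2 at both times, 64 per arm) and assume a correlation r between the preoperative and POD14 scores. The SD is 2 for POD14 alone, 2√(2(1 − r)) for change, and 2√(1 − r²) for ANCOVA.

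| r | Power, POD14 alone | Power, change (SD) | Power, ANCOVA (SD) |
|---|---|---|---|
| 0.2 | 80% | 60% (2.53) | 82% (1.96) |
| 0.5 | 80% | 80% (2.00) | 90% (1.73) |
| 0.7 | 80% | 95% (1.55) | 98% (1.43) |

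Even if 9.1 is read as a between-arm comparison of change, it is therefore a different analysis from the POD14-only comparison. ANCOVA has at least as much power as either across this range.

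**The case against.** The best defence is that the intention is clear. Three sections compare arms, and the relevant item in 9.4.3 is explicitly a between-arm comparison. The 9.1 bullet may be loose wording for change from baseline by arm. Baseline is not ignored either, since 9.4.2 and 9.4.5 already plan a baseline-adjusted ANCOVA. This narrows the point but does not remove it: 9.1 still differs from the other sections, no score is chosen, and the adjusted analysis is only supportive.

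Four stronger readings are tempting and are not supported.

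- **That the two-week Likert analysis will have no data.** Section 9.4.3 itself places the score at that visit, so a site might collect it, and 6.4 mentions a daily pain score. The sentence could also mean that the items just listed are rated on the Likert scale, although its wording favours a separate score. What is shown is a mismatch between the analysis text and the collection lists.
- **That a pre-versus-post test is planned.** No such test appears anywhere in 9.4. The problem is confined to the endpoint wording in 9.1.
- **That the false-positive chance is 18.5%.** That figure, 1 − 0.95⁴, needs four independent tests. The fourth would be the Likert score, whose collection is in doubt and which would probably overlap strongly with the current-pain item.
- **That a promised 5% error rate is broken.** Section 9.4.3 gives a per-test threshold. The plan claims no family-wise control for secondary endpoints.

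Leaving the interference scale out of 9.4.3 is also not an inconsistency, because the synopsis limits the objective to pain levels.

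**Conclusion.** The inconsistency stands, and it concerns a secondary endpoint only. The primary analysis and the 64 per arm are untouched. Three defects are established from the text alone: the 9.1 contrast differs from that in 1.1, 3 and 9.4.3; no lead BPI score is named; and the two-week Likert score in 9.4.3 is missing from the two-week lists in 1.2, 4.1 and 4.4.

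The room for selection is moderate. With the three BPI items each tested at 0.05, the chance of at least one nominally significant result under no effect is about 11% to 12.5% at correlations of 0.7 to 0.5, and 14% under independence. The correlations are assumptions. So are the power figures for the three uses of baseline, which borrow POD1 inputs. The need to settle one definition does not depend on either set of numbers.

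**What to change.** - Use one definition in 1.1, 3, 9.1 and 9.4.3: the between-arm difference at POD14 in one prespecified BPI pain score. The choice is the sponsor's; worst pain in the past 24 hours is one option.
- Analyse it by ANCOVA adjusting for the same score on the preoperative BPI, which is already collected. Amend 9.4.2 and 9.4.5 so that this ANCOVA is the main analysis of that endpoint and not a supportive one.
- Reword the 9.1 bullet as this between-arm comparison.
- Report the other BPI items, and interference if wanted, descriptively.
- Either delete the two-week Likert score from 9.4.3 or add it to the Visit 4 lists. Both reconcile the text.

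**Cost.** Wording changes in about six sections, and fewer formal tests at POD14. No new data are needed if the Likert score is deleted. If it is kept, one more question is asked at an existing visit, and the two-week lists in 1.2, 4.1 and 4.4 need the addition.

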9.2 SAMPLE SIZE DETERMINATION

We used pain score measured at POD1 as our primary outcome of interest. Sample size calculation was calculated using two independent sample t test, under the assumption that the pain scores are normally distributed. At the following test settings:

H_{null} : Mean difference of pain levels reported on a Likert-pain scale by patients between pre- and post-incision arms at POD1 = 0;

H_a : Mean difference of pain levels reported on a Likert-pain scale by patients pre- and post- incision arms at postoperative day one $\neq 0$, and the expected mean difference of pain levels between the two groups is 1 likert point*.

Further we assume,

Standard deviation (std) = 2;

With the following default set-up values:

Alpha = 0.05

Power = 0.8

Weight between study arms = 1 (equal sample size in each arm)

Drop-out rate = 0

The required sample size for the current study is **64 per arm or 128 in total**.

*No well-established mean difference between the two study groups can be found in the literature. Based on clinical observations and experience from physicians that the two different infiltration methods are currently used interchangeably with no obvious difference in patients reported POD1 pain, we hypothesize the likely difference of pain levels between the two study groups to be 1. With standard deviation of 2 (see below), our targeted effect size is 0.5, or a median size effect based on Cohen's rule (Cohen, 1989).

**This SD value was estimated from the study by Yeung et al. (Liposomal Bupivacaine During Robotic Colpopexy VOL. 131, NO. 1, JANUARY 2018) using data from Table 3, average pain with rest at POD1 for the Bupivacaine group. Yeung et al. showed that the mean pain level with rest at POD1 in patients treated with liposomal Bupivacaine was 18.0, with the range of data being 81, on a 100mm-VAS scale. Therefore, a 'rule-of-thumb' of estimating standard deviation: range of data/4 was taken, yielding sd of ~20mm on a VAS scale. This was further translated to a sd of 2 on a 10-point Likert scale as one of the parameters for the sample size calculation for the current study.

9.3 POPULATIONS FOR ANALYSES

Intention to Treat (ITT) and Per Protocol (PP) analysis data sets:

The ITT dataset will consist of all randomized patients. If applicable, a modified ITT (mITT) dataset will consist of all ITT patients who receive the actual assigned timing of infiltration. We expect no protocol violation based on the design of the study. The safety population will consist of all mITT patients.

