7 STUDY INTERVENTION DISCONTINUATION AND PARTICIPANT DISCONTINUATION/WITHDRAWAL

7.1 DISCONTINUATION OF STUDY INTERVENTION

If the first ten patients do not tolerate the study medication, then we will evaluate which adverse reaction the patients experience and as to which arm they were randomized. We will also evaluate at which time point they experienced an adverse reaction and if it was to a preoperative/postoperative medication or if it was to the study drug. Pending the determination of these, we will halt recruitment. It is possible for a patient to discontinue participating in the study after surgery, but not during surgery.

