8.3.4 TIME PERIOD AND FREQUENCY FOR EVENT ASSESSMENT AND FOLLOW-UP

The occurrence of an adverse event (AE) or serious adverse event (SAE) may come to the attention of study personnel during study visits and interviews of a study participant presenting for medical care, or upon review by a study monitor.

All AEs including local and systemic reactions not meeting the criteria for SAEs will be captured on the appropriate case report form (CRF). Information to be collected includes event description, time of onset, clinician's assessment of severity, relationship to study product (assessed only by those with the training and authority to make a diagnosis), and time of resolution/stabilization of the event. All AEs occurring while on study must be documented appropriately regardless of relationship. All AEs will be followed to adequate resolution.

Any medical condition that is present at the time that the participant is screened will be considered as baseline and not reported as an AE. However, if the study participant's condition deteriorates at any time during the study, it will be recorded as an AE.

Changes in the severity of an AE will be documented to allow an assessment of the duration of the event at each level of severity to be performed. AEs characterized as intermittent require documentation of onset and duration of each episode.

[name], co-investigator, will record all adverse events with start dates occurring any time after informed consent is obtained until 7 (for non-serious AEs) or 30 days (for SAEs) after the last day of study participation. At each study visit, the investigator will inquire about the occurrence of AE/SAEs since the last visit. Events will be followed for outcome information until resolution or stabilization.

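### The safety population is defined by adherence to the assigned timing rather than by exposure, so a patient given bupivacaine at the wrong time falls outside it

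*Combined protocol and SAP*

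**What the plan says.** Section 9.3 opens with the line "Intention to Treat (ITT) and Per Protocol (PP) analysis data sets" and then gives three definitions.

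- ITT: "The ITT dataset will consist of all randomized patients".
- Modified ITT, to be formed if applicable: "a modified ITT (mITT) dataset will consist of all ITT patients who receive the actual assigned timing of infiltration".
- Safety: "The safety population will consist of all mITT patients".

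The section also says "We expect no protocol violation based on the design of the study". No set is defined under the per-protocol name.

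Sections 4.1 and 6.1.2 give both arms 0.25% bupivacaine at five trocar sites. The arms differ only in timing.

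Section 9.4.4 (Safety Analyses) describes monitoring: "Assessment of adverse events throughout hospital stay will be done by review of charts and discussion with other members involved in patient care". It names no analysis set and gives no rule for a patient treated otherwise than assigned. Section 8.3.4 requires that "All AEs occurring while on study must be documented appropriately regardless of relationship". Section 9.4.2 does not say which set the t test and the ±1 equivalence rule use.

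**The concern.** A safety population should hold everyone who was exposed. Here the condition for entry is receipt of the assigned timing, which is a per-protocol condition under a modified-ITT name. Anyone injected at the other time fails it despite having received the drug.

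Section 8.4.4 rates the study as greater than minimal risk and lists severe allergic reaction and abnormal heart rhythm among its concerns. A safety denominator that loses exposed patients because of a timing error is hard to defend in such a study, even when the number lost is small.

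The other safety reviews do not make up for this. Section 7.1 looks at affected patients according to "as to which arm they were randomized", and section 10.1.6 speaks of each arm. Neither mentions the timing received.

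**Working it through.** **1. The plan's own figure.** Inputs from section 9.2: difference 1, SD 2, two-sided alpha 0.05, power 0.80, 1:1 allocation, no drop-out. The normal approximation, n per arm = 2(1.960 + 0.842)² × 2² / 1² = 62.8, rounds up to 63. The exact t test gives 63.77, rounded up to 64, with power 0.801. The plan's 64 per arm (128 in total) is reproduced and is not in dispute.

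**2. Following one mistimed patient through the definitions.**

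| Question | Source | Answer |
|---|---|---|
| Received bupivacaine? | 4.1, 6.1.2 | Yes, in either arm |
| In ITT? | 9.3 | Yes, she was randomised |
| In modified ITT? | 9.3 | No, her timing was not the assigned one |
| In the safety population? | 9.3 | No, it equals modified ITT |
| Adverse events recorded? | 8.3.4 | Yes |
| Seen by the medical monitor? | 8.4.4, 10.1.6 | Review is not limited to modified ITT |
| Mistiming reported as a deviation? | 10.1.10 | Yes |
| Restored to a safety analysis set? | 9.4.4 | No set is named |

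**3. Size for safety.** If all 128 are injected and k of them at the non-assigned time, the safety set holds 128 − k. The share of exposed patients left out is k/128: 0.8% for k = 1, 1.6% for k = 2, 2.3% for k = 3.

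The documents give no mistiming rate. As an assumption only, with independent errors at rate p per patient, the chance of at least one is 1 − (1 − p)^128: 12% at p = 0.1%, 47% at 0.5%, 72% at 1%, 92% at 2%.

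**4. What naming ITT as the primary set does to efficacy.** Assume k of the 64 post-incision patients are injected at the pre-incision time and score like that arm, with the SD held at 2. The expected ITT difference is 1 × (1 − k/64): 0.984 for k = 1 and 0.953 for k = 3. The set restricted to assigned timing keeps a difference of 1 with 64 v 64 − k patients. The chance of an equivalence claim is the chance that the 95% confidence interval lies within ±1, integrated over the sampling distribution of the SD.

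| | ITT, k = 1 | Assigned timing, k = 1 | ITT, k = 3 | Assigned timing, k = 3 |
|---|---|---|---|---|
| Power for a 1-point difference | 0.789 | 0.798 | 0.763 | 0.792 |
| Chance of an equivalence claim when the true difference is 1 | 2.75% | 2.5% | 3.35% | 2.5% |

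At a true difference of 0 and k = 3, the chance of the equivalence claim is 60.3% in ITT (64 v 64) and 58.3% in the restricted set (64 v 61).

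**The case against.** The best defence is that little turns on the definition. The plan expects no violation and forms the modified ITT set only if applicable. Sections 6.4 and 8.1 have timing confirmed with the surgeon, and section 9.4.4 plans no safety table or between-arm comparison that would use the set. This stands as a limit on size, and the effect may well be nil. It does not repair the definition. An expectation is not a handling rule, and if the modified ITT set is formed only when a violation occurs, that is exactly when the exclusion takes effect.

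A reader might infer that adverse events in mistimed patients would go unrecorded or unreviewed. The documents say otherwise: sections 8.3.4, 8.4.4, 10.1.6 and 10.1.10 apply whatever the timing received.

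A reader might also infer that withholding the drug during an operation would bias the safety set against post-incision patients. A patient who is never injected is unexposed, and leaving her out of a safety population is normal. The documents give no rate for such cases.

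On the primary efficacy set, section 9.3 lists ITT first and makes the modified set conditional, so ITT is the natural default. That is fair. Section 9.4.2 still needs to say so, but the omission is missing detail and not a second error.

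**Conclusion.** The concern holds as a definitional error in section 9.3. As written, an exposed patient leaves the safety population because of a timing error, and nothing elsewhere in the plan returns her. It should be fixed.

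The practical size is nil without mistiming and 0.8% of 128 patients for each mistimed injection, assuming all 128 are injected. Any statement of how likely this is rests on an assumed rate. The efficacy figures rest on the plan's difference of 1 and SD of 2, with all the errors in one direction. They show only a small effect and do not measure the safety error itself.

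**What to change.** - **Section 9.3, with 9.4.4 referring to it.** Define the safety population as all randomised patients who received any study bupivacaine, tabulated by timing actually received. List adverse events of randomised but uninjected patients separately, by assigned arm.
- **Section 9.3.** Rename the present modified ITT set per protocol, the label its opening line already uses.
- **Section 9.4.2.** State that the primary analysis uses ITT, with the per-protocol 95% confidence interval reported beside it.

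**Cost.** No extra patients and no change to the sample size. Beyond wording, one case report form item for actual timing may be needed, because sections 6.4 and 8.1 describe confirmation with the surgeon but no recorded field.

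If injections are mistimed, ITT gives up a little against the per-protocol set on both power and false equivalence, as tabulated in the working. That is the reason for showing the per-protocol interval beside it.
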